**Table 2: mCRM Design across the Different Scenarios**

Scenario	Percentage of Times the Best MTD Was Truly in the Target Toxicity Range	Percentage of Times at Least One of the Best Two MTDs Was Truly in the Target Toxicity Range	No. of Patients Who Were Treated Above the Target Toxicity Interval (Median [10th, 90th Percentiles])	No. of Patients Who Were Treated at Unacceptable Toxicity (Median [10th, 90th Percentiles])
1	62%	81%	0 [0, 12]	0 [0, 0]
2	67%	81%	0 [0, 3]	0 [0, 0]
3	56%	83%	6 [0, 15]	0 [0, 3]
4	70%	84%	0 [0, 9]	0 [0, 0]

mCRM=modified Continual Reassessment Model; MTD=maximum tolerated dose.

## **Appendix 6**

### **Operating Characteristics of the Modified Continual Reassessment Model for Dose Escalation with Overdose Control (cont.)**

[figure not shown]
Figures 7, 8, 9, and 10 show for Scenarios 1, 2, 3, and 4, respectively, two examples (from the simulations) of how a complete dose escalation (with up to 42 patients) would occur using the proposed mCRM.

As indicated by the results shown in Figures 7, 8, 9, and 10, it can be concluded that the proposed mCRM provides overall very good performance in selecting the correct MTD, while at the same time limiting the amount of overdosing across all scenarios, with the assumed sample size of 42 patients.

## Appendix 6

### Operating Characteristics of the Modified Continual Reassessment Model for Dose Escalation with Overdose Control (cont.)

**Figure 7 Example of Two Complete Trial Realizations in Scenario 1**

[figure not shown]
Ida = idasanutlin; Ven = venetoclax.

Note: Random noise was added to the data along both axis to allow seeing points that otherwise would have overlapped.

## Appendix 6

### Operating Characteristics of the Modified Continual Reassessment Model for Dose Escalation with Overdose Control (cont.)

**Figure 8 Example of Two Complete Trial Realizations in Scenario 2**

[figure not shown]

Ida = idasanutlin; Ven = venetoclax.

Note: Random noise was added to the data along both axis to allow seeing points that otherwise would have overlapped.

## Appendix 6 Operating Characteristics of the Modified Continual Reassessment Model for Dose Escalation with Overdose Control (cont.)

**Figure 9 Example of Two Complete Trial Realizations in Scenario 3**

[figure not shown]

Ida = idasanutlin; Ven = venetoclax.

Note: Random noise was added to the data along both axis to allow seeing points that otherwise would have overlapped.

## Appendix 6 Operating Characteristics of the Modified Continual Reassessment Model for Dose Escalation with Overdose Control (cont.)

Figure 10 Example of Two Complete Trial Realizations in Scenario 4

Ida = idasanutlin; Ven = venetoclax.

Note: Random noise was added to the data along both axes to allow visibility of points that otherwise would have overlapped.

## Appendix 7 ECOG Performance Status Scale

Grade	Description
0	Fully active; able to carry on all pre-disease performance without restriction.
1	Restricted in physically strenuous activity but ambulatory and able to carry out work of a light or sedentary nature (e.g., light housework or office work).
2	Ambulatory and capable of all self-care but unable to carry out any work activities. Up and about > 50% of waking hours.
3	Capable of only limited self-care; confined to a bed or chair > 50% of waking hours.
4	Completely disabled. Cannot carry on any self-care. Totally confined to bed or chair.
5	Dead.

## Appendix 8 Ann Arbor Staging

Grade	Description
Stage I	Involvement of a single lymph node region (I) or of a single extralymphatic organ or site (IE) a
Stage II	Involvement of two or more lymph node regions or lymphatic structures on the same side of the diaphragm alone (II) or with involvement of limited, contiguous extralymphatic organ or tissue (IIE)
Stage III	Involvement of lymph node regions on both sides of the diaphragm (III), which may include the spleen (IIIS) or limited, contiguous extralymphatic organ or site (IIIE), or both (IIIES)
Stage IV b	Diffuse or disseminated foci of involvement of one or more extralymphatic organs or tissues, with or without associated lymphatic involvement

Note: All cases are subclassified to indicate the absence (A) or presence (B) of the systemic B symptoms of significant unexplained fever (> 38°C), night sweats, or unexplained weight loss exceeding 10% of body weight during the 6 months prior to diagnosis.

a The designation "E" generally refers to extranodal contiguous extension (i.e., proximal or contiguous extranodal disease) that can be encompassed within an irradiation field appropriate for nodal disease of the same anatomic extent. A single extralymphatic site as the only site of disease should be classified as IE, rather than Stage IV.

b Involvement of bone marrow at screening will always qualify for Ann Arbor Stage IV and should be recorded as extranodal involvement.

Adapted from:

## Appendix 9 Follicular Lymphoma International Prognostic Index and International Prognostic Index

**Table 1 Follicular Lymphoma International Prognostic Index**

FLIPI Risk Factor	
Ann Arbor Stage III or IV	
Age > 60 years	
Serum LDH > 1 × ULN	
Anemia (hemoglobin < 120 g/L)	
Involved nodal areas > 4	
FLIPI Risk Group	Number of FLIPI Risk Factors
Low	0 or 1
Intermediate	2
High	3 to 5

FDG = fluorodeoxyglucose; FLIPI = Follicular Lymphoma International Prognostic Index;  
PET = positron emission tomography; ULN = upper limit of normal.

Note: The results of FDG-PET should not be taken into account for calculation of FLIPI since this prognostic score was established without FDG-PET.

Adapted from:

## Appendix 9 Follicular Lymphoma International Prognostic Index and International Prognostic Index (cont.)

**Table 2 Follicular Lymphoma International Prognostic Index 2**

FLIPI2 Risk Factor	
Bone marrow involvement	
Age > 60 years	
$\beta_2$ microglobulin > 1 × ULN	
Anemia (hemoglobin < 120 g/L)	
Longest diameter of largest involved node > 6 cm	
FLIPI2 Risk Group	Number of FLIPI2 Risk Factors
Low	0
Intermediate	1 or 2
High	3 to 5

FDG = fluorodeoxyglucose; FLIPI2 = Follicular Lymphoma International Prognostic Index 2; PET = positron emission tomography; ULN = upper limit of normal.

Note: The results of FDG-PET should not be taken into account for calculation of FLIPI2 since this prognostic score was established without FDG-PET.

Adapted from:

## Appendix 9 Follicular Lymphoma International Prognostic Index and International Prognostic Index (cont.)

**Table 3 International Prognostic Index**

IPI Risk Factor	
Ann Arbor Stage III or IV	
Age > 60 years	
Serum LDH > 1 × ULN	
ECOG Performance Status ≥ 2	
Extranodal involvement ≥ 2	
IPI Risk Group	Number of IPI Risk Factors
Low	0 or 1
Low–Intermediate	2
High–Intermediate	3
High	4 or 5

ECOG=Eastern Cooperative Oncology Group; FDG=fluorodeoxyglucose; IPI= International Prognostic Index; PET= positron emission tomography; ULN=upper limit of normal.

Note: The results of FDG-PET should not be taken into account for calculation of IPI since this prognostic score was established without FDG-PET.

Adapted from:

## **Appendix 10 Anaphylaxis Precautions**

### **Equipment Needed**

- Tourniquet
- Oxygen
- Epinephrine for subcutaneous, intravenous , and/or endotracheal use in accordance with standard practice
- Antihistamines
- Corticosteroids
- Intravenous infusion solutions, tubing, catheters, and tape

### **Procedures**

In the event of a suspected anaphylactic reaction during study treatment infusion, the following procedures should be performed:

- Stop the study treatment infusion.
- Apply a tourniquet proximal to the injection site to slow systemic absorption of study treatment. Do not obstruct arterial flow in the limb.
- Maintain an adequate airway.
- Administer glucocorticoids, antihistamines, epinephrine, or other medications as required by patient status and directed by the physician in charge.
- Continue to observe the patient and document observations.

## **Appendix 11**

### **Calculation of Creatinine Clearance Using the modified Cockcroft-Gault Formula**

$$e\text{CCR} = (140 - \text{Age}) \times \text{IBM}^a \text{ (kg)} \times [0.85 \text{ if female}] / (72 \times \text{serum creatinine [mg/dL]})$$

Or, if serum creatinine is in micromoles per liter ( $\mu\text{mol/L}$ ):

$$e\text{CCR} = (140 - \text{Age}) \times \text{IBM}^a \text{ (kg)} \times [1.23 \text{ if male, } 1.04 \text{ if female}] / (\text{serum creatinine} [\mu\text{mol/L}])$$

eCCR = estimated creatinine clearance; IBM = ideal body weight.

a IBM (kg) =  $([\text{height in cm} - 154] \times 0.9) + (50 \text{ if male, } 45.5 \text{ if female})$ .

## **Appendix 12**

### **Recommendations for Initial Management of Electrolyte Imbalances and Prevention of Tumor Lysis Syndrome in the Setting of Treatment with Venetoclax**

#### **First Dose of Venetoclax or a Dose Increase**

- Within the first 24 hours after either the first dose or a dose increase, if any of the following laboratory criteria are met, the patient should be hospitalized for monitoring and the investigator notified. No additional doses of venetoclax should be administered until resolution. A rapidly rising serum potassium level is a medical emergency.
- Nephrology (or acute dialysis service) must be consulted/contacted on admission. (according to institutional standards to ensure emergency dialysis is available).
- Intravenous fluids (e.g., D5 ½ normal saline) should be initiated at a rate of at least 1 mL/kg/hr rounded to the nearest 10 mL (target: 150–200 mL/hr; not < 50 mL/hr).
- Modification of fluid rate should also be considered for individuals with specific medical needs.
- Monitoring for symptoms or signs of tumor lysis syndrome (e.g., fever, chills, tachycardia, nausea, vomiting, diarrhea, diaphoresis, hypotension, muscle aches, weakness, paresthesias, mental status changes, confusion, and seizures)  
If any clinical features are observed, recheck potassium, phosphorus, uric acid, calcium, and creatinine within 1 hour immediately.
- Vital signs should be measured at time of all blood draws or any intervention.

The management recommendations in the following table focus on the minimal initial responses required. If a diagnosis of tumor lysis syndrome is established, ongoing intensive monitoring and multidisciplinary management will be followed according to institutional protocols.

## Appendix 12

### Recommendations for Initial Management of Electrolyte Imbalances and Prevention of Tumor Lysis Syndrome in the Setting of Treatment with Venetoclax (cont.)

Abnormality	Management Recommendations
Hyperkalemia (including rapidly rising potassium)	
Potassium greater than the ULN	
 
• Perform ECG immediately and commence telemetry.
 
• Perform nephrology assessment with consideration of initiating dialysis.
 
• Administer Kayexalate® 60 g (or Resonium A® 60 g).
 
• Administer furosemide 20 mg IV × 1.
 
• Administer calcium gluconate 100–200 mg/kg IV slowly if there is ECG or telemetry evidence of life-threatening arrhythmias.
 
• Recheck potassium, phosphorus, uric acid, calcium, and creatinine in 1 hour STAT.
 
• If potassium is less than the ULN 1 hour later, repeat potassium, phosphorus, uric acid, calcium, and creatinine 1, 2, and 4 hours later if no other evidence of tumor lysis.
 

Potassium ≥0.5 µmol/L increase from prior value (even if potassium is WNL)	
 
• Recheck potassium, phosphorus, uric acid, calcium, and creatinine in 1 hour STAT. If there is a further increase ≥0.2 µmol/L in potassium, but still less than the ULN, manage per potassium greater than the ULN. Otherwise, recheck in 1 hour.
 
• Resume per protocol testing if change in potassium is <0.2 µmol/L and potassium is less than the ULN and no other evidence of tumor lysis.
 
• At the discretion of the investigator, may recheck before hospitalization. If potassium is stable or decreased and still WNL, hospitalization will be at the discretion of the investigator. Potassium, phosphorus, uric acid, calcium, and creatinine must be rechecked within 24 hours.
 

ECG=electrocardiogram; IV=intravenous; STAT=immediately; ULN=upper limit of normal; WNL=within normal limit.

## Appendix 12

### Recommendations for Initial Management of Electrolyte Imbalances and Prevention of Tumor Lysis Syndrome in the Setting of Treatment with Venetoclax (cont.)

Abnormality	Management Recommendations

Hyperkalemia (including rapidly rising potassium) (cont.)
 
Potassium <math>\geq 6.0</math> <math>\mu\text{mol/L}</math> (6.0 mEq/L) and/or patient is symptomatic (e.g., muscle cramps, weakness, paresthesias, nausea, vomiting, and diarrhea)
	
 
• Perform STAT ECG and commence telemetry.
 
• Perform nephrology assessment with consideration of initiating dialysis.
 
• Administer Kayexalate® 60 g (or Resonium A® 60 g).
 
• Administer furosemide 20 mg IV <math>\times 1</math>.
 
• Administer insulin 0.1 U/kg IV + D25 2 mL/kg IV.
 
• Administer sodium bicarbonate 1–2 mEq by IV push. If sodium bicarbonate is used, rasburicase should not be used as this may exacerbate calcium phosphate precipitation.
 
• Administer calcium gluconate 100–200 mg/kg IV slowly if there is ECG or telemetry evidence of life-threatening arrhythmias. Do not administer in same IV line as sodium bicarbonate.
 
• Recheck potassium, phosphorus, uric acid, calcium, and creatinine every hour STAT.
 

Hyperuricemia
 
Uric acid <math>\geq 8.0</math> mg/dL (476 <math>\mu\text{mol/L}</math>)
	
 
• Consider rasburicase (dose per institutional guidelines). If rasburicase is used, sodium bicarbonate should not be used as this may exacerbate calcium phosphate precipitation.
 
• Recheck potassium, phosphorus, uric acid, calcium, and creatinine in 1 hour STAT.
 

ECG=electrocardiogram; IV=intravenous; STAT=immediately; ULN=upper limit of normal; WNL=within normal limit.

## Appendix 12

### Recommendations for Initial Management of Electrolyte Imbalances and Prevention of Tumor Lysis Syndrome in the Setting of Treatment with Venetoclax (cont.)

Abnormality	Management Recommendations

Hyperuricemia (cont.)
 
Uric acid <math>\geq 10</math> mg/dL (595 <math>\mu\text{mol/L}</math>)  or            uric acid <math>\geq 8.0</math> mg/dL (476 <math>\mu\text{mol/L}</math>) with 25% increase and creatinine increase <math>\geq 0.3</math> mg/dL (<math>\geq 0.027</math> <math>\mu\text{mol/L}</math>) from pre-dose level
	
 
• Administer rasburicase (dose per institutional guidelines).
 
If rasburicase is used, sodium bicarbonate should not be used as this may exacerbate calcium phosphate precipitation.
 
• Consult nephrology.
 
• Recheck potassium, phosphorus, uric acid, calcium, and creatinine in 1 hour STAT.
 
• If uric acid <math>< 8.0</math> mg/dL 1 hour later, repeat potassium, phosphorus, uric acid, calcium, and creatinine 2 and 4 hours later if no other evidence of tumor lysis.
 

Hypocalcemia
 
Calcium <math>\leq 7.0</math> mg/dL (1.75 <math>\mu\text{mol/L}</math>)  and            patient is symptomatic (e.g., muscle cramps, hypotension, tetany, cardiac arrhythmias)
	
 
• Administer calcium gluconate 50–100 mg/kg IV slowly with ECG monitoring.
 
• Perform telemetry.
 
• Recheck potassium, phosphorus, uric acid, calcium, and creatinine in 1 hour STAT.
 
• If calcium normalized 1 hour later, repeat potassium, phosphorus, uric acid, calcium, and creatinine 2 and 4 hours later if no other evidence of tumor lysis.
 
• Calculate corrected calcium and check ionized calcium if albumin is low.
 


Hyperphosphatemia
 
Phosphorus <math>\geq 5.0</math> mg/dL (1.615 <math>\mu\text{mol/L}</math>) with <math>\geq 0.5</math> mg/dL (0.16 <math>\mu\text{mol/L}</math>) increase
	
 
• Administer a phosphate binder (e.g., aluminum hydroxide, calcium carbonate, sevelamer hydroxide, or lanthanum carbonate).
 
• Notify nephrology dialysis required for phosphorus <math>\geq 10</math> mg/dL)
 
• Recheck potassium, phosphorus, uric acid, calcium, and creatinine in 1 hour STAT.
 
• If phosphorus <math>< 5.0</math> mg/dL 1 hour later, repeat potassium, phosphorus, uric acid, calcium, and creatinine 2 and 4 hours later if no other evidence of tumor lysis.
 

ECG = electrocardiogram; IV = intravenous; STAT = immediately; ULN = upper limit of normal; WNL = within normal limit.

## Appendix 12

### Recommendations for Initial Management of Electrolyte Imbalances and Prevention of Tumor Lysis Syndrome in the Setting of Treatment with Venetoclax (cont.)

Abnormality	Management Recommendations
Hyperphosphatemia (cont.) Creatinine Increase $\geq 25\%$ from baseline	
 
• Start or increase rate of IV fluids.
 
• Recheck potassium, phosphorus, uric acid, calcium, and creatinine in 1–2 hours STAT.
 

ECG=electrocardiogram; IV=intravenous; STAT=immediately; ULN=upper limit of normal; WNL=within normal limit.

#### Ongoing Dosing with Venetoclax

Management of electrolyte changes from last value at >24-hour intervals after either the first dose or dose increase (e.g., 48 or 72 hours) is described below. Note: If the patient is hospitalized, no additional doses of ventoclax should be administered until resolution.

- For potassium, admit patient for any increase  $\geq 1.0 \mu\text{mol/L}$  (1.0 mEq/L) or any level greater than the ULN.  
Refer to the management guidelines for electrolyte changes observed within the first 24 hours after either the first dose or a dose increase (see table).
- If a smaller increase in potassium is observed that does not meet the criteria for admission above, recheck potassium, phosphorus, uric acid, calcium, and creatinine within 24 hours and confirm no evidence of tumor lysis before further venetoclax dosing.
- For uric acid, calcium, phosphorus, and creatinine, refer to the management guidelines for electrolyte changes observed within the first 24 hours after either the first dose or dose increase (see table).

## Appendix 13

## 1 Introduction

The purpose of this document is to define the specifications required for the analyses and output production for the InHarmony studies (BO29561, BO29562, BO29563, GO29833, GO29834, BH29812). This document should be referred to alongside the harmonized List of Planned Outputs (LoPO) spreadsheet.

## 2 Data Handling Specifications

### 2.1 Datacut

For primary CSR analyses, each study will have data cut based on the 'clinical cutoff date' (CCOD). Data collected on or before the CCOD will be included in.

For the datacut rules refer to the instructions for 'fixed-cutoff datacut' type on the Global Data Standards Repository (GDSR) Browser - [Rules and Definitions for Analysis Data Cuts](#).

### 2.2 Treatment Definition

"Chemotherapy" (CT) is defined as at least one dose > 0 of Doxorubicin, Bendamustine, Cyclophosphamide, Vincristine or Prednisone/Prednisolone/Methylprednisolone (=steroids). Steroids are only counted as part of Chemotherapy if they were given as part of CHOP according to the study drug eCRF page (EX domain).

"Study treatment" is defined as at least one dose > 0 of any component of combination therapy (e.g. obinutuzumab, atezolizumab, polatuzumab vedotin, venetoclax, lenalidomide, idasanutlin) or chemotherapy.

#### 2.2.1 Treatment Groups

The treatment arm labels to be included in the outputs are displayed as described below in following order:

Atezolizumab will be replaced by 'Atezo'

Obinutuzumab will be replaced by 'G'

Rituximab will be shown as 'R'

Polatuzumab vedotin will be replaced by 'P'

Venetoclax will be replaced by 'V'

Idasanutlin will be replaced by 'I'

Lenalidomide will be replaced by 'L'

Bendamustine will be replaced by 'B'

CHOP will be shown as 'CHOP'

We also should show dose levels after each treatment. So for illustration purposes, a treatment arm of "Obinutuzumab 1000mg + Polatuzumab vedotin 1mg/kg + Lenalidomide 10mg" would be shown as "G (1000MG) P (1MG/KG) L (10MG)", or "Obinutuzumab 1000mg + Atezolizumab 1mg + CHOP" would be shown as "Atezo (1MG) - G (1000MG) - CHOP".

### **2.2.2 New Anti-lymphoma Treatment**

A new anti-lymphoma treatment (NALT) is defined as any treatment reported on the 'Follow-up New Anti-Lymphoma Therapy' or 'New Anti-Lymphoma Surgery and Procedure' eCRF pages.

If a patient has more than one, use the first date from any of the NALTs.

## **2.3 Patient Allocation to Reporting Periods**

The following definitions will be used to allocate AEs and laboratory data to study periods. The same definitions will also be used in other cases where applicable, e.g. patient disposition. Adverse events are assigned to the study periods based on the AE onset date.

### **2.3.1 Study Day 1**

Study day 1 is the day of first administration of any study treatment (see Section 2.2).

### **2.3.2 Before Therapy**

Any AE that occurs before study day 1 is considered to have occurred before therapy unless the end date is after the date of first study drug intake and the most extreme intensity is higher than the initial intensity (see treatment emergent rules in Section [6.2.1](#)). For handling of pre-dose laboratory assessments, see definition of baseline (Section 2.3.3).

### **2.3.3 Baseline**

The baseline assessment is the last valid assessment in the 28 day window before first administration of a study treatment component (see Section 2.2 for study treatment definition). If no time is linked to a laboratory or vital sign assessment at study day 1, it is assumed that the assessment was done before the drug administration. For patients who never received study treatment, baseline is defined as the last valid assessment prior to or on the day of enrolment – note though that this is only applicable to parameters not being reported out using the safety population, as otherwise these patients are anyway excluded.

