##### **4.5.1 Informed Consent Forms and Screening Log**

Written informed consent for participation in the study must be obtained before performing any study-related procedures. Informed Consent Forms for enrolled patients and for patients who are not subsequently enrolled will be maintained at the study site.

All screening evaluations must be completed and reviewed to confirm that patients meet all eligibility criteria before enrollment. The investigator will maintain a screening log to record details of all patients screened and to confirm eligibility or record reasons for screening failure, as applicable.

Results of standard-of-care tests or examinations performed prior to obtaining informed consent, and within the defined window, may be used as screening and baseline assessments (see [Appendix 1](#) and [Appendix 2](#)); such tests do not need to be repeated for screening purposes (e.g., screening tumor assessment).

Study treatment should be initiated within 28 days after the Informed Consent Form has been signed. Those patients who fail screening based on longer waiting times for certain results or due to study technical reasons (such as cohort on hold) can be rescreened once at a later date if they were deemed eligible before the screen failure. The decision to rescreen individual patients will be made jointly by the Roche Medical Monitor and the investigator and any other person the investigator or Medical Monitor considers necessary to assist with this decision. Any such decision and the reasons for

it will be clearly documented. Any out-of-window assessments need to be repeated and undergo a complete review by the Roche Medical Monitor.

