#### **4.5.5.2 Bone Marrow Assessments**

Bone marrow assessments, consisting of bone marrow biopsy and aspiration, are required at screening for staging purposes in all patients and should be performed within approximately 3 months prior to Day 1 of Cycle 1.

For patients with bone marrow involvement at screening, a repeat assessment will be performed if there is radiologic evidence of a complete response or if clinically indicated (e.g., if there is clinical suspicion of progressive disease in the bone marrow with no radiologic evidence of progression) (see [Appendix 1](#) for details).

Any additional (unscheduled) bone marrow assessments performed during the study will be at the discretion of the investigator.

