### Schedule of Activities for Patients with Follicular Lymphoma: Dose-Escalation and Expansion Phases (cont.)

---

- x Refer to [Appendix 3](#) for detailed schedule.
- y Includes circulating lymphoma cells and/or cell-free circulating-tumor DNA.
- z Includes B-cell counts (CD19), T-cell counts (CD3, CD4, and CD8), and natural killer cell counts (CD16 and CD56).
- aa Requires separate patient consent for RBR participation. Not applicable for a site that has not been granted approval for RBR sampling.
- bb Availability of adequate archival or freshly biopsied tumor tissue samples should be confirmed at screening (see Section [4.5.6](#) for details).
- cc A tumor biopsy sample is preferred and recommended at the time of progression unless no adequate tumor site is accessible.
- dd After informed consent has been obtained but prior to initiation of study treatment, only serious adverse events caused by a protocol-mandated intervention should be reported. After initiation of study treatment, all adverse events will be reported until 90 days after the last dose of study treatment. After this period, the Sponsor should be notified if the investigator becomes aware of any serious adverse event that is believed to be related to prior study treatment (see Section [5.6](#)). An exception is made for Grade 3 and 4 infections (related and unrelated) in patients who received obinutuzumab, which should be reported until up to 2 years after the last dose of study treatment. The investigator should follow each adverse event until the event has resolved to baseline grade or better, the event is assessed as stable by the investigator, the patient is lost to follow-up, or the patient withdraws consent. Every effort should be made to follow all serious adverse events considered to be related to any of the study treatment components or trial-related procedures until a final outcome can be reported.
- ee The screening PET-CT scan must be performed within 35 days prior to Day 1 of Cycle 1.
- ff Perform only for patients who receive at least two cycles of induction treatment.
- gg If PET-CT scan is positive at the EOI, perform 12 months after initiation of induction treatment, within 14 days prior to study treatment administration.

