- hh CT scan of the neck (if clinically indicated), chest, abdomen and pelvis. If contrast is medically contraindicated (e.g., patients with contrast allergy or impaired renal clearance), MRI scans of the chest, abdomen, and pelvis (and neck, if clinically indicated) and a non-contrast CT scan of the chest may be performed. Combined PET/CT scanners may be used to collect diagnostic CT scans but only according to the technical guidelines in the imaging manual. Screening CT scan must be performed within 35 days prior to Day 1 of Cycle 1.
- ii Perform within 7 days prior to Day 1 of Cycle 3.
- jj Perform 12, 18, and 24 months after initiation of induction treatment, within 14 days prior to treatment administration.
- kk Perform only if not done within the previous 3 months.
- ll Perform every 6 months.
- mmm Bone marrow biopsy and aspirate must be performed within approximately 3 months prior to Day 1 of Cycle 1.
- nn For patients with bone marrow involvement at screening, a repeat assessment will be performed at the EOI, during maintenance, or at the EOM whenever there is radiologic evidence of a complete response or if clinically indicated (e.g., if there is clinical suspicion of progressive disease in the bone marrow with no radiologic evidence of progression). Additional bone marrow assessments may be performed at the discretion of the investigator.

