## 10.57 Output 57 ECG Results Shift Table

Treatment x (N=xx)

Shift TO: ECG Result at Visit	Shift FROM: Baseline			Total
	Abnormal, clinically significant	Abnormal, not clinically significant	Normal	
END OF INDUCTION COMPLETION / DISCONTINUATION				
Abnormal, clinically significant	0	0	0	0
Abnormal, not clinically significant	0	xx (xx.xx%)	xx (xx.xx%)	xx (xx.xx%)
Normal	0	xx (xx.xx%)	xx (xx.xx%)	xx (xx.xx%)
Total	0	xx (xx.xx%)	xx (xx.xx%)	xx (xx.xx%)
END OF MAINTENANCE COMPLETION / DISCONTINUATION				
Abnormal, clinically significant	0	0	0	0
Abnormal, not clinically significant	0	xx (xx.xx%)	0	xx (xx.xx%)
Normal	0	0	0	0
Total	0	xx (xx.xx%)	0	xx (xx.xx%)

Baseline assessment is the last valid assessment in the 28 day window before first administration of a study treatment component.

Programing notes:

1. Analysis population: Safety
2. Template ID: EGT01
3. Program name: T\_EG\_CB
4. Analysis variables: Electrocardiogram (ECG)

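### The SAP's 28-day baseline window is shorter than the protocol's screening windows for scans and bone marrow, so protocol-valid tumour baselines can be lost from descriptive outputs

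*SAP*

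**What the plan says.** **SAP.** Section 2.3.3 states: "The baseline assessment is the last valid assessment in the 28 day window before first administration of a study treatment component". The SAP defines baseline nowhere else. Section 2.3 introduces its definitions for adverse events and laboratory data, then widens them: "The same definitions will also be used in other cases where applicable, e.g. patient disposition". Output 57 (ECG) repeats the rule: "Baseline assessment is the last valid assessment in the 28 day window before first administration of a study treatment component".

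Section 4.2 lists, as baseline items, the counts of indicator and non-indicator lesions, SPD, bulky disease, PET score and FDG-avid disease. Outputs 67 and 68 plot percentage change from baseline in indicator lesion size.

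**Protocol.** Appendix 1 (FL) says of PET-CT: "The screening PET-CT scan must be performed within 35 days prior to Day 1 of Cycle 1". For CT it says: "Screening CT scan must be performed within 35 days prior to Day 1 of Cycle 1". For marrow it says: "Bone marrow biopsy and aspirate must be performed within approximately 3 months prior to Day 1 of Cycle 1". Appendix 2 sets the same three windows for DLBCL. Section 4.5.5.2 repeats that marrow assessments "should be performed within approximately 3 months prior to Day 1 of Cycle 1". Section 4.5.1 adds: "Results of standard-of-care tests or examinations performed prior to obtaining informed consent, and within the defined window, may be used as screening and baseline assessments".

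**The concern.** The two documents use different look-back periods for the same assessments. A scan or marrow result can qualify a patient for the study and still fail the SAP's definition of baseline.

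A patient whose only screening scan is too old for the SAP has no baseline lesion size. That patient then either disappears from the baseline tumour-burden summaries and the two change-from-baseline plots, or is rescued by a programming decision that nobody has written down. In cohorts of about 40, a few such patients would visibly change the denominators of those outputs.

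**Working it through.** The plan gives no figure on this point to reproduce. The check compares the windows and then illustrates the size.

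**Step 1. Same anchor.** The SAP counts back from the first dose of any study treatment component, the protocol from Cycle 1 Day 1. Every regimen gives an antibody on Cycle 1 Day 1, including Regimen B, where obinutuzumab is given alone in Cycle 1. The anchors therefore coincide and the windows can be subtracted.

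**Step 2. Days accepted by the protocol but not by the SAP.**

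| Assessment | Protocol window | SAP window | Days outside the SAP window | Share of protocol window |
|---|---|---|---|---|
| PET-CT, CT | 35 days | 28 days | 35 - 28 = 7 (Day -35 to Day -29) | 7/35 = 20% |
| Marrow | about 3 months: 3 × 30.4375 ≈ 91 days | 28 days | 91 - 28 = 63 | 63/91 ≈ 69% |

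The factor 30.4375 is the SAP's own days-to-months conversion (2.3.9). These are shares of days, not of patients.

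**Step 3. Can a compliant patient fall in the gap?** Yes. Protocol 4.5.1 wants treatment started within 28 days of consent, and the schedules place scans and marrow in the Day -28 to Day -1 column. A scan done for the study will therefore normally fall inside 28 days. But 4.5.1 also accepts pre-consent standard-of-care results within the defined window, and names the screening tumour assessment as an example of a test that need not be repeated. A sole scan on Day -35 to Day -29 is therefore allowed.

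**Step 4. Illustrative size.** The documents do not give the timing of screening scans. Let p be the assumed proportion of patients whose only screening scan falls in the gap, with n = 40 per expansion cohort (protocol 6.1.2). The expected number is np, and the chance of at least one is 1 - (1 - p)^40.

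| Assumed p | Expected of 40 | Chance of at least one per cohort |
|---|---|---|
| 5% | 2 | 1 - 0.95^40 = 87% |
| 10% | 4 | 1 - 0.90^40 = 98.5% |
| 20% | 8 | 1 - 0.80^40 > 99.9% |

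**Step 5. With the protocol windows used for these assessments,** the excluded days fall from 7 and about 63 to zero.

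**The case against.** **The rule was meant for laboratory data.** Section 2.3 opens with adverse events and laboratory data, 2.3.2 points to 2.3.3 for pre-dose laboratory values, and the tumour outputs do not restate the 28 days. Section 4.2 also lists tissue biomarkers at baseline, although the protocol accepts archival tissue, so a literal 28-day limit would remove those as well. This makes it doubtful that the authors intended the rule for every baseline item. It does not change what the rule says:

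- The first sentence of 2.3.3 is unrestricted; only the next one is about laboratory and vital-sign timing.
- Its last sentence, on never-treated patients, refers to parameters not reported on the safety population. Output 11, the baseline disease table, is reported on the ITT population.
- Output 57 applies the rule to ECG.
- No other baseline definition is available for imaging.

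**Few patients are exposed.** This stands. Only pre-consent results with no later repeat are normally at risk. A reader might turn the 20% and 69% of days into 8 of 40 patients without a scan baseline and more than half without a marrow baseline. That assumes dates spread evenly over the windows, which the screening column and the 28-day limit from consent to treatment contradict.

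**Marrow involvement may escape the rule.** This also stands. SAP 4.2 does not tag bone marrow involvement as a baseline-dated item, and Output 11 draws on history and prognostic-factor pages, so it may be reported without any date window.

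**The primary endpoint.** Because a PET-CT CR requires normal marrow in patients with marrow involvement at baseline, a reader might infer that the primary CR rate is at risk. The documents do not support this. The IRC and the investigator apply that criterion when they assign response (protocol 4.5.5 and Appendix 4), and SAP 5.1 takes the IRC's determination as given. It does not pass through 2.3.3.

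**Conclusion.** The conflict is real. Followed literally, SAP 2.3.3 discards screening scans from Day -35 to Day -29 that the protocol accepts. Patients with no later pre-dose scan lose their baseline for lesion counts, SPD, bulky disease and PET variables, and their place in the waterfall and spider plots. For marrow the conclusion is conditional: involvement is affected only if it is derived by assessment date.

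The consequence is confined to descriptive outputs; no response rate, confidence interval or survival endpoint is shown to change. The number of patients is unknown, and the 2, 4 or 8 of 40 rest entirely on the assumed 5%, 10% or 20%.

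Two further assumptions apply. SAP section 1 does not list BH39147 among its studies, so its application here is inferred from the tables in 6.2.2, which do include it. Which section 4.2 items are actually produced depends on the separate list of planned outputs, which is not among the documents.

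**What to change.** Amend SAP 2.3.3 so that baseline depends on the type of assessment:

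- For tumour imaging, bone marrow and tissue-based disease characteristics, use the last valid pre-dose assessment accepted under the protocol's screening rules.
- For laboratory, vital-sign and ECG data, keep the 28-day window.

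Referring to the protocol's screening rules avoids programming a cutoff of approximately 3 months. It also keeps archival-tissue biomarkers, which a blanket 28 days for everything other than scans and marrow would remove.

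The cost is about one sentence in the SAP and a change to the baseline derivation. No new data are needed. It should be settled before the baseline disease and tumour-change outputs are programmed.
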